Study Center(s)	This multicenter retrospective case series will be conducted at approximately 40 sites.	
Objectives	This study is intended to provide large-scale, real-world data on clinical outcomes with DEXYCU (dexamethasone intraocular suspension) 9%.	
Number of Subjects	Total of up to 600 subjects across all sites.	
Eligibility Criteria and main objective	To be eligible, patients must have received a dose of DEXYCU at the close of ocular surgery.	
Study Interventions and Measures	Review of medical records. Collection of patient characteristics, clinical outcomes, and patient and practitioner satisfaction.	
Statistical Methodology	Descriptive statistics will be performed for data collected.	

1 Background and Study Rationale

This study is a retrospective case study/chart review. The study will be reviewed and approved by an independent institutional review board and will be conducted in accordance with International Council for Harmonisation/Good Clinical Practice requirements as well as applicable federal and state regulations.

1.1 Study Introduction

DEXYCU (dexamethasone intraocular suspension) 9% was approved by the United States of America Food and Drug Administration (FDA) in 2018 for the treatment of postoperative inflammation. This study was initiated in order to obtain information on the drug's performance in real-world clinical practice.

1.2 Background and Relevant Literature and Data

The FDA approval of DEXYCU was based on prospective, randomized, controlled clinical trials in patients undergoing cataract surgery. After cataract and other ocular surgeries, inflammation is typically controlled with topical corticosteroid and/or non-steroidal anti-inflammatory drug (NSAID) drops. As an intraocular, sustained-release formulation of dexamethasone, DEXYCU may be able to replace routine postoperative topical corticosteroid drops. As an intraocular, sustained-release formulation of dexamethasone, DEXYCU may be able to replace routine postoperative topical corticosteroid drops.

However, the phase 3 trials evaluating the safety and efficacy of DEXYCU excluded a number of clinical scenarios and aspects of perioperative management likely to be encountered in day-to-day practice. For example, though cataract and glaucoma may often coexist, most patients with glaucoma or ocular hypertension were excluded from clinical trials of DEXYCU, and its use has not been studied in minimally-or micro-invasive glaucoma surgery (MIGS) procedures, which are commonly paired with cataract surgery in patients with glaucoma.^{4,5} Similarly, patients experiencing certain intraoperative complications (e.g., posterior capsule rupture) that may not preclude the use of DEXYCU in clinical practice were also excluded from the clinical trials. The concomitant use of postoperative NSAIDs and corticosteroids (topical or intraocular) is routine,³ but adjunctive NSAIDs constituted a protocol violation in DEXYCU clinical studies unless pre-specified anti-inflammatory rescue criteria had been met.^{1,2} Finally, details about the administration of the DEXYCU droplet and its behavior in the eye were limited in the clinical trials and are of interest to collect.

DEXYCU is not only newly available, it is also different in kind from other ophthalmic corticosteroids indicated for treating postoperative inflammation, given that it is the only FDA-approved intraocular formulation. Thus, there is a particular need for data on the performance of DEXYCU in real-world practice, without the restrictions that are necessary for randomized, prospective trials. A retrospective case study allows this data to be obtained relatively rapidly and at scale, so that it may be made available to interested practitioners and published in the medical literature.

2 Study Objectives

This study is intended to provide large-scale, real-world data on clinical outcomes with DEXYCU. The purpose is to collect and summarize data on the clinical performance of DEXYCU in terms of anti-inflammatory efficacy, tolerability, intraocular behavior of the product, and patient satisfaction as reported to the surgeon and surgeon satisfaction.

3 Study Design and Methods

3.1 General Study Design

This is a retrospective chart review study for subjects previously treated with DEXYCU.

3.1.1 Total Number of Subjects

The study will enroll up to 600 subjects at approximately 40 sites.

3.2 Study Population

3.2.1 Inclusion Criteria

- Male and Female subjects at least 18 years of age
- Subjects who underwent cataract surgery from 12Mar2019 to 15Oct2019 and received DEXYCU

3.2.2 Exclusion Criteria

Subjects who underwent cataract surgery and did not receive DEXYCU

4 Study Procedures

This study will involve the review of existing medical records.

4.1 Date Range of the study

Cases will be included in the study if they underwent cataract surgery and received DEXYCU between 12 March 2019 and 15 October 2019.

4.2 Subject Selection

Subjects will be identified for inclusion in the study by participating investigators/surgeons according to their medical discretion.

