4.4 Variable Abstraction

Patient Characteristics: Patient ID – Assigned as entered into Fusion (this is not the subject's medical record number) Patient Demographics including Age at the time of surgery, Gender, Ethnicity, Race Medical History including risk factors, Diabetes and Glaucoma Surgery Details: Affected Eyes, location of cataract and severity Date of surgery with DEXYCU Type of surgery

CONFIDENTIAL

This material is the property of EyePoint Pharmaceuticals.

Intraocular lens (IOL) manufacturer, location and model
Viscoelastic usage
DEXYCU placement
Visibility of DEXYCU and Timing of DEXYCU
DEXYCU adherence
Concomitant Medications
Were any preoperative, intraoperative, or postoperative medications taken?
Clinical Outcomes Timepoints (POD 1, 8, 14, 30 and Unscheduled):
DEXYCU visibility
Anterior chamber cells (ACC)
Anterior chamber flare (ACF)
Intraocular pressure (IOP)
BCVA
UCVA
Rank efficacy vs topical steroids
Target Visual Acuity (VA) achieved
Product Tolerated
Patient and Surgeon Satisfaction:
Patient Satisfaction with DEXYCU based on feedback to the Surgeon
Surgeon Satisfaction with DEXYCU
Ease of use
Postoperative regimen
DEXYCU time efficiency for physicians and staff
Other Remarks

5 Statistical Plan

Descriptive statistics will be performed for de-identified demographic data, surgical details, clinical outcomes, and surgeon and patient satisfaction.

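### Section 4.2 lets surgeons choose already treated, eligible cases by undefined medical discretion, and the plan has no sampling rule and no count of eligible cases left out

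*Combined protocol and SAP*

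**What the plan says.** - **Who picks cases.** Section 4.2: "Subjects will be identified for inclusion in the study by participating investigators/surgeons according to their medical discretion". Nothing says what this discretion covers.
- **Who is eligible.** Section 3.2 requires age 18 or over and cataract surgery with DEXYCU in the date window. The only exclusion is not having received DEXYCU. Section 4.1 adds: "Cases will be included in the study if they underwent cataract surgery and received DEXYCU between 12 March 2019 and 15 October 2019".
- **How many.** Section 3.1.1: "The study will enroll up to 600 subjects at approximately 40 sites". There is no rule for which cases fill that number.
- **When picking happens.** Section 3.1: "This is a retrospective chart review study for subjects previously treated with DEXYCU". Section 4: "This study will involve the review of existing medical records".
- **What is recorded.** Section 4.4 includes "Patient Satisfaction with DEXYCU based on feedback to the Surgeon" as well as the surgeon's own satisfaction.
- **Analysis.** Section 5: "Descriptive statistics will be performed for de-identified demographic data, surgical details, clinical outcomes, and surgeon and patient satisfaction".

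The text available for review contains no consecutive or random rule, site quota, screening log or tally of eligible cases that were not abstracted.

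**The concern.** In a chart review, treatment and follow-up may be over before a case is chosen. No treatment decision remains for medical discretion to govern, so in practice the phrase gives the surgeon a free choice of charts. A surgeon who also treated the patient may already know how the eye did and how satisfied the patient was, and these are among the results to be reported.

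No hypothesis test is at stake, because the study is openly a descriptive case series. But the descriptive rates are its whole product. Section 2 presents them as large-scale evidence of performance in ordinary practice, and section 1.2 intends them for publication. Section 1.2 also justifies the study by patients whom the phase 3 trials left out: those with glaucoma, with MIGS procedures or with intraoperative complications. If such cases, or cases with poor results, were passed over or sought out, nothing planned would reveal it. A reader could not tell whether a rate describes treated cases or chosen ones.

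**Working it through.** **1. The plan's own figure.** There is nothing to reproduce. The 600 is a ceiling with no power or precision target behind it. Equal shares would be 600/40 = 15 subjects per site.

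**2. The sections side by side.** Sections 3.2 and 4.1 say who may enter, 3.1.1 sets a ceiling, and 4.2 says who decides. If a site has more eligible subjects than it enters, only 4.2 governs which ones go in, and 4.2 states no criterion.

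**3. How far outcome-related selection could move a rate.** The documents give no outcome rates and no eligible volume, so the following are assumptions: the true rate p of a poor outcome; the ratio r of the chance that a poor-outcome chart is picked to the chance that a good-outcome chart is picked; and an intraclass correlation of 0.02 within sites. From the documents: 40 sites, and n = 600 as the ceiling. A sample of n = 300 is also assumed, in case the ceiling is not reached.

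- Reported rate: o = p·r / (p·r + 1 − p)
- 95% half-width: 1.96·√(D·o(1 − o)/n)
- D = 1 without clustering. With clustering, D = 1 + (n/40 − 1)·0.02, which is 1.28 at n = 600 and 1.13 at n = 300.

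Example: p = 0.10 and r = 0.5 give o = 0.05/(0.05 + 0.90) = 5.26%, a bias of −4.74 points. The half-width at n = 600 without clustering is 1.96·√(0.0526·0.9474/600) = 1.79 points.

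The half-width is only a yardstick, since the plan names no confidence intervals. The range shown runs from n = 600 unclustered to n = 300 clustered. The last column counts the four combinations of n and clustering.

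| True p | r | Reported | Bias (points) | Half-width (points) | Bias exceeds half-width |
|---|---|---|---|---|---|
| 5% | 0.5 | 2.6% | −2.44 | 1.26 to 1.90 | 4 of 4 |
| 5% | 0.75 | 3.8% | −1.20 | 1.53 to 2.30 | 0 of 4 |
| 5% | 1.33 | 6.6% | +1.56 | 1.98 to 2.98 | 0 of 4 |
| 10% | 0.5 | 5.3% | −4.74 | 1.79 to 2.69 | 4 of 4 |
| 10% | 0.75 | 7.7% | −2.31 | 2.13 to 3.21 | 1 of 4 |
| 10% | 0.9 | 9.1% | −0.91 | 2.30 to 3.46 | 0 of 4 |
| 10% | 1.33 | 12.9% | +2.90 | 2.68 to 4.03 | 1 of 4 |
| 20% | 0.5 | 11.1% | −8.89 | 2.51 to 3.78 | 4 of 4 |
| 20% | 0.75 | 15.8% | −4.21 | 2.92 to 4.39 | 3 of 4 |
| 20% | 0.9 | 18.4% | −1.63 | 3.10 to 4.66 | 0 of 4 |
| 20% | 1.33 | 25.0% | +5.00 | 3.46 to 5.21 | 3 of 4 |

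At p = 2%, moderate selection (r = 0.75 or 1.33) exceeds the half-width in 0 of 8 settings, and r = 0.5 does so in 2 of 4. A larger sample narrows the half-width but leaves the bias as it is.

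**4. What a count would add.** If a fraction f of eligible cases is abstracted and the reported rate is o, the rate in all eligible cases lies between f·o and f·o + (1 − f), whatever the selection. For an assumed o of 10%:

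- f = 0.9: 9.0% to 19.0%
- f = 0.75: 7.5% to 32.5%
- f = 0.5: 5.0% to 55.0%

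The count is informative when capture is high and says little when it is low. As planned, f is not recorded at all.

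**The case against.** Several points on the other side carry weight.

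- **Sections 4.1 and 4.2 need not contradict each other.** A reader might infer a contradiction, because 4.1 taken alone admits every qualifying case. But 4.1 sits under a date-range heading, gives no order of entry, and has to be read with a ceiling of 600. It can be read as eligibility only. The two sections need aligned wording, and the point does not depend on a conflict between them.
- **Section 4.2 may only mean that surgeons judge which charts qualify.** The text does not exclude this. The section's heading and the word discretion make it the weaker reading, and even so no rule says which qualifying charts fill the ceiling.
- **A reader might infer that surgeons will favour good outcomes.** The documents support no such statement. They neither describe nor forbid choice by outcome, and a surgeon could equally favour difficult cases.
- **A reader might infer that the bias could never be detected or bounded.** That goes too far. The records exist, and a list might be built later. What can be said is that none is planned.
- **The arithmetic rests on assumed inputs.** This stands. How often bias exceeds sampling error depends on the rates chosen, and at low event rates moderate selection does not exceed it. The table shows what is possible and is not evidence of what occurred.
- **This is an openly descriptive case series.** That limits the stakes, and labelling the results as investigator-selected would remove much of the risk of misreading. It would not tell a reader how selected the cases are.

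**Conclusion.** The point holds as a weakness in the selection rule that should be fixed. It does not stop the study. As written, surgeons choose among eligible, already treated cases by an undefined criterion, possibly knowing the outcome, and the plan collects nothing that would show whether the choice was related to outcome.

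The size is unknown. Strong selection (r = 0.5) would outweigh sampling error at true rates of 5%, 10% and 20%. Moderate selection would do so only in some settings at 10% and 20%, and in none at 5%. Mild selection (r = 0.9) would not at 10% or 20%. All of this rests on assumed outcome rates, selection ratios and clustering; only the 600 and the 40 come from the documents. The absence of a sampling rule or log is judged on the text available for review.

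**What to change.** State that sections 3.2 and 4.1 together set eligibility: adults who had cataract surgery with DEXYCU in the date window. The Synopsis speaks of ocular surgery more broadly and should be reconciled with these sections, since the list depends on the definition. Then replace section 4.2 with:

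> Each site lists all eligible subjects from its records, and abstracts all of them or, above a site maximum set in advance, a consecutive or random sample drawn without reference to outcome. The numbers listed, abstracted and omitted, with reasons, are reported by site.

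Three details go with it:

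- **Counting unit.** Say whether it is the subject or the eye. The ceiling is in subjects, but section 4.4 records affected eyes.
- **Site maximum.** The documents give none, so it must be set beforehand. Where sampling fractions then differ between sites, report site-weighted rates (weights from the numbers listed) as well as unweighted rates.
- **Charts already chosen, or no list possible.** Describe those results as investigator-selected.

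**Cost.** Sites need time to build lists at about 40 centres. The hours cannot be estimated, because section 4.3 does not say whether records can be searched for DEXYCU use. Surgeons lose the choice of charts, and a random sample may bring in charts with less complete follow-up. The ceiling of 600 does not change.

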4.3 Data Sources

Data will be found in paper or electronic medical records at study sites.

4.4 Variable Abstraction

Patient Characteristics: Patient ID – Assigned as entered into Fusion (this is not the subject's medical record number) Patient Demographics including Age at the time of surgery, Gender, Ethnicity, Race Medical History including risk factors, Diabetes and Glaucoma Surgery Details: Affected Eyes, location of cataract and severity Date of surgery with DEXYCU Type of surgery

CONFIDENTIAL

This material is the property of EyePoint Pharmaceuticals.

Intraocular lens (IOL) manufacturer, location and model
Viscoelastic usage
DEXYCU placement
Visibility of DEXYCU and Timing of DEXYCU
DEXYCU adherence
Concomitant Medications
Were any preoperative, intraoperative, or postoperative medications taken?
Clinical Outcomes Timepoints (POD 1, 8, 14, 30 and Unscheduled):
DEXYCU visibility
Anterior chamber cells (ACC)
Anterior chamber flare (ACF)
Intraocular pressure (IOP)
BCVA
UCVA
Rank efficacy vs topical steroids
Target Visual Acuity (VA) achieved
Product Tolerated
Patient and Surgeon Satisfaction:
Patient Satisfaction with DEXYCU based on feedback to the Surgeon
Surgeon Satisfaction with DEXYCU
Ease of use
Postoperative regimen
DEXYCU time efficiency for physicians and staff
Other Remarks

5 Statistical Plan

Descriptive statistics will be performed for de-identified demographic data, surgical details, clinical outcomes, and surgeon and patient satisfaction.
